### **6.2 Full Analysis Set (FAS)**

The FAS includes all randomized subjects who had a Baseline Visit 1 at Day 0 and at least one post-dose in-clinic assessment with the 4-point scale by either the investigator or the subject on visits at Weeks 1, 2, or 4. Within the FAS a subject will be considered for the treatment assigned by randomization and not for the treatment actually received, if different, i.e., following the intent-to-treat principle. The FAS will be used for the evaluation of the efficacy assessments. The FAS serves as the primary efficacy analysis set.

### **6.3 Protocol Deviations**

Protocol deviations and exclusions of subjects from analysis sets will be identified at the Data Review Meeting (DRM) just prior to study unblinding for the Final Analysis.

Deviations from the protocol will be classified as major or minor.

The following protocol deviations are considered a priori to be major:

- Subject or investigator unblinded to treatment
- Improper storage of IMP and IMP temperature excursion without proper notice to the CRA
- Incorrect treatment allocation or dose
- Wrong injection points used

### **6.4 Blinded Data Review Meeting (BDRM)**

Subjects will be assigned to the SAF and FAS during the BDRM. For the BDRM appropriate listings displaying all relevant data will be provided to the Sponsor and serve as a source for the protocol deviations discussion about the classification into major and minor. No unblinding will be done for the creation of these listings.

Details for and decisions on protocol deviations will also be discussed at the BDRM, taking place between database lock and unblinding. Corresponding documentation should be held outside of the SAP.

Unblinding will be done after the BDRM has been conducted and the minutes have been signed.

## 7 STATISTICAL CONSIDERATIONS AND ANALYSIS

### 7.1 Derived Variables

The below table provide the list of derived variables for various duration derivations and Baseline derivations applicable for this study.

Variables	Formula
Derivation of Duration	
Study day at any visit	Date of interest – date of first dose of study drug, if date of interest is before date of first dose of study drug. Date of interest – date of first dose of study drug + 1, otherwise.
Baseline Derivations	
Baseline	The Baseline value is defined as the last observation before treatment, i.e., pre-treatment values measured on the treatment day (Baseline visit, Day 0), and if missing or not evaluated, the value from the screening visit will be used. Baseline will be missing if no values have been measured before treatment.
Change from Baseline	Post-Baseline value – Baseline value
Relative change from Baseline	[(Post-Baseline value – Baseline value)/Baseline value]*100

### 7.2 Handling of Missing Data

#### 7.2.1 Missing Data Analysis Methods

Analyses will be performed by visit. The main analysis will be performed based on all available data. That is, no imputation of missing values will be conducted (e.g., no last observation carried forward), except for estimating the response rate at Week 4 for the co-primary endpoints where subjects with missing FWS assessments at Baseline or Week 4 will be considered as non-responders.

For all other visits and endpoints, summary statistics will be based on observed data.

### **7.2.2 Handling of Missing or Incomplete Dates**

#### **7.2.2.1 Imputation Rules for Missing or Partial AE Start Date:**

##### **If only Day of AE start date is missing:**

If the AE start year and month are the same as that for the first dose date, then:

- If the full (or partial) AE end date is NOT before the first dose date or AE end date is missing, then impute the AE start day as the day of first dose date; otherwise, impute the AE start day as 1.
- Otherwise, impute the AE start day as 1.

Otherwise, if the AE start year and month are not the same as that for the first dose date, then impute the AE start day as 1.

Compare the imputed AE start date with the first dose date to determine whether the AE is pre-treatment AE or treatment emergent adverse event (TEAE).

##### **If Day and Month of AE start date are missing:**

If AE start year = first dose year, then:

- If the full (or partial) AE end date is NOT before the first dose date or AE end date is missing, then impute the AE start Month and Day as the Month and Day of first dose date; otherwise, impute the AE start Month as January and the Day as 1.
- Otherwise, impute the AE start MONTH as January and the DAY as 1.

Compare the imputed AE start date with TE period to determine whether the AE is pre-treatment AE, TEAE or post-treatment AE.

##### **If Year of AE start date is missing:**

If the year of AE start is missing or AE start date is completely missing then query site with no imputation. Also compare the full (or partial) AE end date to the first dose date. If the AE end date is before the first dose date then the AE should be considered as a pre-treatment AE. Otherwise, the AE will be considered as TEAE.

### **7.2.2.2 Imputation Rules for Missing or Partial Medication Start/Stop Dates**

#### **Missing or partial medication start date:**

- If only DAY is missing, use the first day of the month.
- If DAY and Month are both missing, use the first day of the year.
- If DAY, Month and Year are all missing, use a date before the first dose date.

#### **Missing or partial medication stop date:**

- If only DAY is missing, use the last day of the month.
- If DAY and Month are both missing, use the last day of the year.
- If DAY, Month and year are all missing, assign ‘continuing’ status to stop date

If the resultant imputed stop date is later than the death date, revise the imputed stop date as the death date.

## 8 STATISTICAL METHODS

### 8.1 General Statistical Conventions

All statistical procedures will be completed using SAS version 9.4 or higher.

The statistical analysis will be performed after database lock of all data up to the end of the study.

Unless otherwise stated, all statistical testing will be two-sided and will be performed using a significance (alpha) level of 0.05. A two-sided CI using the Newcombe method (using a significance level of 0.05) will be provided for the difference in treatment effects between proportions at week 4. Two-sided 95% confidence intervals (CI) will be provided within individual treatment groups when relevant.

No formal statistical hypothesis testing will be conducted.

Continuous variables will be summarized using descriptive statistics, including number of subjects (n), mean, median, standard deviation (SD), minimum and maximum. One additional decimal point for mean and median and two additional decimal points for SD will be used in addition to the number of decimal points used for the measured values.

For categorical variables, summaries will include counts of subjects and percentages. Percentages will be rounded to one decimal place.

For statistical analyses, “baseline” refers to the last observation before treatment, i.e. pre-treatment values measured on the treatment day (Baseline visit, Day 0), and if missing or not evaluated, values from screening visit will be used. Baseline will be missing if no values have been measured before treatment.

All summaries will be presented by treatment group, unless otherwise specified.

Analyses will be performed by visit, irrespective of any time window deviations.

All subject data, including those derived, will be presented in individual subject data listings. Unless otherwise stated, unscheduled visit results will be included in date/time chronological order, within patient listings only. All listings will be sorted by investigational site, patient number, date/time and visit. The treatment group (Test, Reference) will be stated on each listing. Unless otherwise stated, data listings will be based on the SAF. A listing with demographic data for screening failures will be presented.

### 8.2 Subject Disposition

Subject disposition information will be summarized by treatment group and overall. The number and percent of subjects who are randomized, who obtained a dose of study drug, who were randomized and not treated, who were treated and not randomized, who complete the treatment, who complete the study and who withdraw early from the study will be presented.

The primary reason for early withdrawal will also be tabulated.

Subject disposition will be listed.

The number and percent of subjects in each analysis set will also be tabulated.

Treatment Misallocations:

If a subject was:

- Randomized but not treated, then they will be reported under their randomized treatment group for efficacy analyses. However, they are by definition excluded from the safety analyses as actual treatment is missing.
- Treated but not randomized, then by definition they will be excluded from the efficacy analyses since they are not randomized but will be included in safety analyses.
- Randomized but got incorrect treatment, then they will be reported under their randomized treatment group for all efficacy analysis, but will be reported under the treatment they actually received for all safety analyses.

## 8.3 Protocol Deviations

The number of subjects excluded from SAF, and FAS populations and reasons for exclusion will be summarized by treatment group and overall.

Analysis set membership details will be listed, including reason for exclusion from each analysis set.

All major protocol deviations identified will be summarized by treatment group and overall. Minor protocol deviations will be listed only.

A listing will include the inclusion/exclusion criteria violated at Screening and at the Baseline visit as well as other protocol deviations identified based on data recorded on the electronic CRF (eCRF) and/or protocol deviation logs from [REDACTED] (based on All Subjects).

## 8.4 Demographics and Baseline Characteristics

### 8.4.1 Baseline Characteristics

The categorical baseline characteristics such as pregnancy test results at screening will be summarized using frequency counts for the FAS population. Continuous Baseline variables such as systolic blood pressure (mmHg), diastolic blood pressure (mmHg) and pulse rate (beats/min) will be summarised by descriptive statistics in the same way as continuous demographic variables for the FAS population.

### 8.4.2 Demographics

Age, age groups, sex, race, ethnicity, height, weight, and Fitzpatrick skin type at Baseline will be summarized descriptively by treatment group and overall using the FAS population. The FDA guideline regarding “Collection of race and ethnicity data in clinical trials” will be followed.

### 8.4.3 Medical History

A summary of medical history will be presented by system organ class (SOC) and preferred term (PT) using Medical Dictionary for Regulatory Activities® (MedDRA) Version 22.0 or higher. The table will be based on the SAF population. The previous toxin treatment will be listed only.

### 8.4.4 Prior and Concomitant Medications

Medications used in this study will be coded by using the latest available version of the World Health Organization Drug Dictionary Standard or Enhanced and categorized as follows:

Prior medications and concomitant medications will be summarized descriptively using frequency tables by anatomical therapeutic chemical (ATC) class and preferred name by treatment group on the FAS population and presented separately for the following groups:

- Medication (recent) discontinued prior to Baseline (Day 0)
- Concomitant medication started at or after Baseline, or started before Baseline and were not discontinued prior to Baseline

Details for imputing missing or partial start and/or stop dates of medication are described in [Section 7.2.2](#).

An individual subject listing will be provided for prior and concomitant medications data.

## 8.5 Extent of Exposure

### 8.5.1 Treatment Duration

Duration of study drug (in days) will not be calculated as subjects will receive only one dose on Day 0.

Planned and actual dose as well as injections at all sites per subject will be listed.

### 8.5.2 Treatment Compliance

All study procedures are to be performed under supervision at the study site, and thus, no separate procedures will be used to monitor subject compliance.

## 8.6 Efficacy Analyses

### 8.6.1 Analysis Methods

The analyses of the primary and secondary outcome measures will be exploratory in nature. Details for each efficacy endpoint will be provided in the following sections. Subgroup analyses will be described in [Section 8.8.1](#).

#### 8.6.1.1 Multiplicity

Since the focus of the statistical analysis is on descriptive statistics and no formal statistical hypothesis testing is planned, no adjustment for controlling the type 1 error rate for the co-primary endpoints is required. Thus, analyses will be considered only exploratory.

### 8.6.2 Analysis of Primary Efficacy Endpoints

The purpose of the study is to provide preliminary comparative efficacy and safety data of BoNT/A-DP versus [REDACTED]

The study comprises co-primary endpoints defined as:

- An FWS score of 0 or 1 and a  $\geq 1$  point reduction in FWS score at maximum frown at the Week 4 Visit relative to Baseline, based on investigator assessment.

That is, a subject will be considered a responder if they have an FWS score of 0 or 1 and an improvement  $\geq 1$  point at maximum frown of the glabellar lines at Week 4 relative to Baseline in FWS, based on the investigator assessment.

- An FWS score of 0 or 1 and a  $\geq 1$  point reduction in FWS score at maximum frown at the Week 4 Visit relative to Baseline, based on subject assessment.

That is, a subject will be considered a responder if they have an FWS score of 0 or 1 and an improvement  $\geq 1$  point at maximum frown of the glabellar lines at Week 4 relative to Baseline in FWS, based on the subject assessment.

No formal statistical hypothesis testing will be conducted and no adjustment for controlling the type 1 error rate for the co-primary endpoints is required.

The focus of the statistical analysis for the co-primary endpoints will be on descriptive statistics (n and %), and 95% CIs for the difference in treatment effects between BoNT/A-DP and [REDACTED]

Two-sided 95% CIs using the Newcombe method will be calculated for the difference between BoNT/A-DP and [REDACTED] for each co-primary endpoint. Two-sided 95% CIs for the responder rates in the BoNT/A-DP and the [REDACTED] treatment groups will be calculated using Wilson scores. No formal statistical hypothesis testing will be conducted.

The FAS population will serve as the primary analysis set for the descriptive statistics.

For the investigator assessment, subjects with missing FWS investigator assessment at Baseline or at the Week 4 Visit will be assigned as non-responders.

For the subject assessment, subjects with missing FWS subject assessment at Baseline or at the Week 4 Visit will be assigned as non-responders.

## **Additional Analyses on the Co-Primary Efficacy Endpoint Variables:**

- The co-primary endpoint measures will also be summarized using the observed values only

For the investigator assessment, subjects with missing FWS investigator assessment at Baseline or at the Week 4 Visit will be excluded from analysis but not assigned as non-responders.

For the subject assessment, subjects with missing FWS subject assessment at Baseline or at the Week 4 Visit will be excluded from analysis but not assigned as non-responders.

The same analyses as described for the co-primary endpoints above will be conducted for the additional analyses.

In addition, subgroup analyses will be conducted as described in [Section 8.8](#).

### **8.6.3 Analysis of Secondary Efficacy Endpoints**

Since the focus of the statistical analysis is on descriptive statistics and no formal statistical hypothesis testing is planned on secondary endpoints, no adjustment for controlling the type 1 error rate is required.

For the below categorical endpoints,

- Percentage of responders with an FWS score of 0 or 1 and a  $\geq 1$  point reduction in FWS score at maximum frown at Weeks 1, 2, 8, 12 and 16, based separately on independent investigator assessments and subject assessments
- Percentage of responders with an FWS score of 0 or 1 and a  $\geq 2$  point reduction in FWS score at maximum frown at Weeks 1, 2, 4, 8, 12 and 16, based separately on independent investigator assessments and subject assessments
- Percentage of responders with an FWS score of 0 or 1 and a  $\geq 1$  point reduction in FWS score at rest at Weeks 1, 2, 4, 8, 12 and 16, based separately on independent investigator

assessments and subject assessments

the same analyses will be conducted as described for the co-primary endpoints.

For investigator assessments, subjects with missing FWS investigator assessment at Baseline or at the post-Baseline visit will be assigned as non-responders.

For subject assessments, subjects with missing FWS subject assessment at Baseline or at the post-Baseline visit will be assigned as non-responders.

The analyses of these secondary endpoints will also be conducted on observed values.

For investigator assessments, subjects with missing FWS investigator assessment at Baseline or at the post-Baseline visit will be excluded from the analysis but not assigned as being non-responders.

For subject assessments, subjects with missing FWS subject assessment at Baseline or at the post-Baseline visit will be excluded from the analysis but not assigned as being non-responders.

Appropriate descriptive statistics will be provided for the secondary endpoint analyses.

The following secondary endpoints will be analyzed descriptively using Kaplan-Meier time to event methodology

- Time to onset of effect, as measured at Weeks 1, 2, and 4, based separately on independent investigator assessments and subject assessments. Onset of effect is defined as  $\geq 1$  point improvement in Glabellar Line Scale - Investigator (GLS-I) and Glabellar Line Scale – Subject (GLS-S) score relative to Baseline at maximum frown in glabellar lines. In addition, onset of effect will be assessed by subjects daily during the first 2 weeks after treatment, by recordings in the subject diary.
- For subjects who respond, duration of effect will be assessed separately based on independent investigator assessments and subject assessments. Effect will be deemed to be lost when scores return to individual Baseline values.

Duration of effect is defined as the date that loss of response occurred – date of IMP Injection

+1. Whereas the loss of response is considered when the response returns to the individual “baseline” grade or worse for Week 4 responder (defined as by having achieved FWS score of 0 or 1 and a  $\geq 1$  point reduction in FWS score at maximum frown at the Week 4 Visit) on FWS at maximum frown. For example, if a subject has a Baseline FWS of 3, the loss of response will be considered when the post-Baseline FWS returns to 3. Duration of effect will be derived separately based on investigator assessments and subject assessments.

For responders that maintain response, censoring will be done at the last visit where FWS grade at maximum frown is assessed.

Survival statistics such as the Kaplan-Meier estimator of the median will be presented.

The FACE-Q assessment at Weeks 4, 12 and 16 will be analyzed descriptively (n and % will be presented).

The FACE-Q Satisfaction with Outcome Scale will be derived in accordance with the developers' instructions and missing data treated accordingly.

The FAS population will serve as the primary analysis set for the descriptive statistics.

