## 10. SUBJECT SELECTION, WITHDRAWAL AND DISCONTINUATION

### 10.1 Inclusion Criteria

Subjects who meet **ALL** of the following criteria are eligible for this study:

- 18 - 75 years of age, inclusive, at the time of Screening.
- Has moderate to severe glabellar frown lines at maximum frown (severity score of 2 or 3 on GLS-I/GLS-S) as determined in-clinic assessments by both the investigator and subject (where: 0='none', 1='mild', 2='moderate', 3='severe').
- Subject has a stable medical condition with no uncontrolled systemic disease.
- Female subjects of childbearing potential must test negative for pregnancy and agree to use highly effective birth control during the course of the study.
- Subjects who wear glasses must be able to adequately self-assess the severity of their glabellar lines (according to the GLS-S), without glasses obstructing the forehead area.

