## 13. ASSESSMENT OF EFFICACY

### 13.1 Assessment of Glabellar Line Severity: Facial Wrinkle Scale

In accordance with FDA Guidelines for Upper Facial Lines, efficacy will be determined using well defined, valid and reliable clinician-reported and subject-reported assessments, capable of measuring the critical outcomes that contribute to a conclusion of overall success or failure. For both investigator and subject assessment, measurements will be made at maximum frown (the worst appearance of upper facial lines with maximum load on the muscle; eyebrows pushed together as far as they can go) and at rest (the best appearance of upper facial lines with the least load on the muscle), which allows one to impute benefit when the face is in dynamic motion (variable load on the muscle).

The scale used most frequently in clinical studies is the FWS, which is a four-point rating scale as follows: 0=no facial wrinkles; 1=mild facial wrinkles; 2=moderate facial wrinkles; and 3=severe facial wrinkles. The scale has been validated and shown to be reproducible. However, this scale includes pictures at rest and at maximum frown within the one scale, meaning that the sensitivity of the scale at rest is low. The FWS proposed for use in this study is comprised of the GLS-I and GLS-S. The scales and the instructions for use for the investigator and subject are provided in [Section 23.1](#) and [Section 23.2](#), respectively; additional information for the investigator is provided in the completion manuals: ‘Glabellar Line Scale - Subject: Completion Manual for Investigator’, and ‘Glabellar Line Scale - Investigator: Completion Manual’.

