#### **15.4.2 Secondary Outcome Measures**

##### **Key Secondary Analyses:**

Since the focus of the statistical analysis is on descriptive statistics and no formal statistical hypothesis testing is planned on secondary endpoints, no adjustment for controlling the type 1 error rate is required.

The following are considered key secondary endpoints:

1. Percentage of responders with an FWS score of 0 or 1 and a  $\geq 1$  point reduction in FWS score at maximum frown at Weeks 1, 2, 8, 12 and 16, based on independent investigator assessment and subject assessment.
2. Percentage of responders with an FWS score of 0 or 1 and a  $\geq 2$  point reduction in FWS score at maximum frown at Weeks 1, 2, 4, 8, 12 and 16, based on independent investigator and subject assessments.
3. Percentage of responders with an FWS score of 0 or 1 and a  $\geq 1$  point reduction in FWS score at rest at Weeks 1, 2, 4, 8, 12 and 16, based on independent investigator and subject assessments.
4. Time to onset of effect, as measured at Weeks 1, 2, and 4, based on independent investigator and subject assessments. Onset of effect is defined as  $\geq 1$  point improvement in Glabellar Line Scale - Investigator (GLS-I) and Glabellar Line Scale – Subject (GLS-S) score relative to Baseline at maximum frown in glabellar lines. In addition, onset of effect will be assessed by subjects daily during the first 2 weeks after treatment, by recordings in the subject diary.
5. For subjects who respond, duration of effect will be assessed based on independent investigator and subject assessments. Effect will be deemed to be lost when scores return to Baseline values.
6. The FACE-Q assessment at Weeks 4, 12 and 16.

For categorical endpoints, the same analyses will be conducted as described for the co-primary endpoints. Continuous variables will be summarized using the following descriptive statistics: number of subjects (n), mean, standard deviation, median, minimum and maximum. 95% confidence of the difference in treatment effects will be calculated. Time-to-response and duration of response will be analyzed using Kaplan-Meier methodology.

The FACE-Q Satisfaction with Outcome Scale will be derived in accordance with the developers' instructions and missing data treated accordingly.

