**Table 2: Schedule of Study Assessments**

Procedures and Visit No	Screening  (Day -14 to 0)	Randomization  (Baseline, Day 0)	Week 1 (± 2 days)	Week 2 (± 5 days)	Week 4 (± 2 days)	Week 8 (± 5 days)	Week 12 (± 5 days)	Week 16 (± 5 days)	End of Study 
	1	2	3	4	5	6	7	8	
Informed consent	x								
Inclusion/exclusion criteria	x	x 							
Medical history	x								
Demographics	x								
Pregnancy test 	x	x			x	x	x	x	
Physical	x								x
Vital signs 	x	x	x		x		x	x	
Concomitant	x	x	x	x	x	x	x	x	
GLS-I 	x	x	x	x	x	x	x	x	
GLS-S 	x	x	x	x	x	x	x	x	
Photography 	x			x	x		x	x	
Treatment					x		x	x	
IMP administration		x							
Post-treatment obs./AE & AESI assessment 		x							
AE and AESI 		x	x	x	x	x	x	x	
Subject diary		D	R/	R					

1. Screening and Baseline, including randomization and treatment, can be done on the same day. If Screening and Baseline are done on the same day, assessments only need to be performed once.
2. For subjects that are prematurely discontinued from the study (at any time), the End of Study visit will take place within one week of discontinuation.
3. If Screening and Baseline are done on different days, the following inclusion and exclusion criteria are to be re-confirmed at Baseline: investigator and subject assessment of glabellar line severity at maximum frown using GLS-I and GLS-S, respectively, as well as documentation of medical history, concomitant medications and AEs.
4. Pregnancy testing for all women of childbearing potential: Screening, Baseline (if Screening and Baseline are done on different days), and End of Study.  
All pregnancy testing will be urine dip stick testing.
5. Additional pregnancy testing (urine dipstick) for women of childbearing potential in Austrian sites, only.
6. Vital signs include blood pressure (diastolic /systolic) and pulse.
7. Investigator's assessment of glabellar line severity at maximum frown and at rest. Assessment will be made using the 4-point GLS-I: (0 =none, 1=mild, 2=moderate, 3=severe). Results will be recorded in the eCRF.
8. Subject's assessment of glabellar line severity at maximum frown and at rest. Assessment will be made using the 4-point GLS-S: (0 =none, 1=mild, 2=moderate, 3=severe). Results will be recorded in the eCRF.
9. Photographs to be taken of subject's glabellar lines at maximum frown and at rest.

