### 8.8 Other Analysis

#### 8.8.1 Subgroup Analysis

The following subgroup analyses will be performed for the co-primary efficacy endpoints:

- a) Subgroup analysis by site
- b) Subgroup analysis by Country
- c) Subgroup analysis by Geographic Region (Europe and US/Canada)
- d) Previous use of Botulinum
- e) Subgroup analysis by race (American Indian or Alaskan Native, Asian, Black or African American, Native Hawaiian or Other Pacific Islander, Caucasian (Including Hispanic or Latino and Other))
- f) Subgroup analysis of:
  - subjects with previous use of botulinum toxin by site
  - naïve subjects by site
- g) Subgroup analysis by Fitzpatrick skin type (TYPE I, TYPE II, TYPE III, TYPE IV, TYPE V, and TYPE VI)
- h) Subgroup analysis by sex
- i) Subgroup analysis by ethnicity (Hispanic or Latino versus Not Hispanic or Not Latino)
- j) Subgroup analysis by age groups (below 65 years, 65-74 years and  $\geq$  75 years)
- k) Subgroup analysis by additional age groups (below 65 years versus 65 years and older).

Subgroup analyses will be performed on the FAS population. Two-sided 95% CIs using the Newcombe method will be calculated for the difference between BoNT/A-DP and [REDACTED]. Two-sided 95% CIs for the responder rates in the BoNT/A-DP and the [REDACTED] treatment groups will be calculated using Wilson scores, when relevant.

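### At-rest responder rates count subjects with no resting lines at Baseline, who cannot respond; show the rate among subjects who can respond beside them

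*SAP*

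**What the plan says.** SAP 8.6.3 lists three responder rules, two at maximum frown and one at rest. The at-rest rule needs a score of 0 or 1 and at least a 1 "point reduction in FWS score at rest at Weeks 1, 2, 4, 8, 12 and 16, based separately on independent investigator" and subject ratings. It is analysed like the co-primary endpoints: counts, percentages, Wilson intervals by arm and a Newcombe interval for the difference. Missing ratings count as non-response, and a second version uses observed values only. For the denominator, "The FAS population will serve as the primary analysis set for the descriptive statistics".

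The severity criterion in Protocol 10.1 is "Has moderate to severe glabellar frown lines at maximum frown (severity score of 2 or 3 on GLS-I/GLS-S" by both raters. When Screening and Baseline fall on different days, the Baseline re-check in SAP Table 2 covers "investigator and subject assessment of glabellar line severity at maximum frown using GLS-I and GLS-S, respectively". Neither text sets a minimum score at rest, although both raters also score rest on the same 0 to 3 scale at every assessment visit. Protocol 13.1 describes the resting state as "at rest (the best appearance of upper facial lines with the least load on the muscle".

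Protocol 15.4.2 introduces the group containing the at-rest endpoint with "The following are considered key secondary endpoints". SAP 8.6.1.1 says of the plan as a whole: "Thus, analyses will be considered only exploratory".

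**The concern.** The at-rest rule needs room to fall by a point, and nothing in eligibility guarantees that room. A subject with frown lines at full contraction but none at rest is eligible, belongs in the FAS, and is a certain non-responder at rest at all six visits.

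A low at-rest rate could then mean a weak effect or simply few resting lines, and the planned display does not separate the two. The cap depends on each rater's own Baseline scores, so it can differ between the investigator and subject results. It does not arise at maximum frown for eligible subjects. The at-rest rates are therefore not on the same footing across raters or beside the maximum-frown rates, and the difference between products is diluted.

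Nothing else in the SAP addresses this. The FAS definition (6.2) has no resting-score condition. The observed-values version drops only missing ratings, and a Baseline 0 is not missing. The subgroup section is limited to the primary endpoints ("The following subgroup analyses will be performed for the co-primary efficacy endpoints"), and none of its factors is Baseline severity. Section 9 is silent. Section 8.4.1 does not name the resting score.

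**Working it through.** **1. The plan's own figure.** SAP section 5 gives a half-width of 10.8% for 100 per group and 81.5% in both. 1.96 × √(2 × 0.815 × 0.185 / 100) = 0.1076, so it reproduces. The Newcombe interval also gives ±10.8 points. The figure is not written for the at-rest endpoint.

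**2. Which follow-up scores count as response**

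| Rule | Baseline 0 | 1 | 2 | 3 |
|---|---|---|---|---|
| Maximum frown, ≥1 point | not eligible | not eligible | 0, 1 | 0, 1 |
| Maximum frown, ≥2 points | not eligible | not eligible | 0 | 0, 1 |
| Rest, ≥1 point | none | 0 | 0, 1 | 0, 1 |

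Only the at-rest rule has an admissible Baseline score from which response is impossible.

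**3. Effect on the estimate.** Let q be the share at Baseline 0 (equal in both arms) and r1, r2 the response rates among the rest.

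- Whole-FAS rate = (1−q) × r, with maximum 1−q.
- Whole-FAS difference = (1−q) × (r1 − r2).
- The ratio r1/r2 is unchanged.

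Neither q nor any at-rest rate is in the documents. The table assumes 60% v 45% and 100 per arm, with Newcombe 95% intervals in percentage points. The subset has 100 × (1−q) per arm.

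| q | Cap | Whole-FAS difference | Baseline ≥1 difference |
|---|---|---|---|
| 5% | 95% | 14.25 (0.4 to 27.3) | 15 (0.8 to 28.4) |
| 10% | 90% | 13.5 (−0.3 to 26.6) | 15 (0.4 to 28.7) |
| 30% | 70% | 10.5 (−2.8 to 23.3) | 15 (−1.5 to 30.4) |
| 50% | 50% | 7.5 (−4.7 to 19.4) | 15 (−4.4 to 32.9) |

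**4. Raters.** If one rater scores 20% of subjects 0 at rest and the other 40%, the same 60% response among those who can respond reads as 0.80 × 60 = 48% and 0.60 × 60 = 36%.

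**5. Chance imbalance.** Randomization balances q on average only. At q = 30% the 95% range of the between-arm difference in q is ±1.96 × √(2 × 0.3 × 0.7 / 100) = ±12.7 points. With r = 60% in both arms, a 10-point imbalance alone puts 0.60 × 10 = 6 points into the whole-FAS difference.

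**6. Precision.** For equal products the whole-FAS half-width is widest, 13.6 points, where (1−q) × r = 50%. At r = 60% it goes from 13.3 (q = 0) through its peak near q = 17% to 12.6 (q = 50%). The interval therefore does not move one way with q, and precision is not the argument for the change.

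**The case against.** The best defence is that the whole-FAS rate is a legitimate quantity and is what the protocol specifies. The trial enrols people defined by lines at maximum frown, and the share of them who gain at rest is a fair question. The planned contrast is between arms within a rater, where randomization removes directional bias. No planned analysis compares raters, or rest with maximum frown. All of that stands, and it is why the whole-FAS result should stay.

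The proposed subset is also imperfect. Its denominators differ by rater, a Baseline 1 must still reach 0 to respond, and the interval is wider: 31.9 against 26.2 points at 60% v 45% and q = 30%. Six visits, two raters and two missing-data versions would add 6 × 2 × 2 = 24 contrasts to an exploratory endpoint. These are real costs.

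Some of the information may appear elsewhere. The list in SAP 8.4.1 is given as examples, the table templates are a separate document, SAP 8.1 lists all subject data, and Protocol 7.5.1.1 foresees post-hoc sensitivity analyses. A Baseline table or listing could reveal q, but none of these pre-specifies the between-arm contrast among subjects who can respond.

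Finally, the size is entirely assumed. At q = 5% the two displays hardly differ. That limits the claim without removing it, because q is unknown until it is tabulated.

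**Conclusion.** The point holds as a modest improvement. A rater's Baseline score of 0 at rest rules out response for that rater at every visit, and the plan neither sets such subjects apart nor provides a result without them. The whole-FAS rate is valid, with no directional bias and an unchanged ratio of rates. It is capped at 1−q, and its difference is shrunk by 1−q.

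Under the assumed 60% v 45%, the 15-point difference reads as 13.5, 10.5 or 7.5 points at q = 10%, 30% or 50%, if q is equal in both arms. At 30% and 50% both displays have intervals that include zero. The effect is negligible if q is small. No test or margin depends on this endpoint, so no decision changes.

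**What to change.** - In SAP 8.4.1, add the Baseline at-rest score distribution (0, 1, 2, 3) by arm and rater. If only one item is taken up, this is the most useful, because it shows q.
- In SAP 8.6.3, keep the whole-FAS at-rest result. Beside it give the responder rates, difference and Newcombe interval in FAS subjects whose Baseline at-rest score by the same rater is at least 1, with the subset size by arm.
- Handle missing post-Baseline ratings in the subset as 8.6.3 already does: non-responder in one version, excluded in the other. Subjects still without a Baseline at-rest score after the Screening fallback in SAP 7.1 stay in the whole-FAS version only.
- Record the addition in SAP section 9, preferably before unblinding. If it comes later, describe it in the CSR, as SAP section 1 requires for deviations.

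The cost is short SAP text, one filter, one Baseline table and one extra set of at-rest tables. The scores are already collected, no protocol change is needed, and no type 1 error adjustment is involved. The price is smaller, rater-specific denominators and wider absolute intervals.
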